7.3.2.4 Life-threatening

An adverse event or suspected adverse reaction is considered *life-threatening* if, in the view of either the investigator or sponsor, its occurrence places the patient or subject at immediate risk of death. It does not include an adverse event or suspected adverse reaction that, had it occurred in a more severe form, might have caused death.

7.4 Recording of an Adverse Event

All grade 3 and above adverse events will be recorded using the NCI CTCAE v4.0. The Investigator will assign attribution of the possible association of the event with use of the investigational drug.

Relationship	Attribution	Description
Unrelated to investigational drug/intervention	Unrelated	The AE is clearly NOT related to the intervention
	Unlikely	The AE is doubtfully related to the intervention
Related to investigational drug/intervention	Possible	The AE may be related to the intervention
	Probable	The AE is likely related to the intervention
	Definite	The AE is clearly related to the intervention

Signs or symptoms reported as adverse events will be graded and recorded by the Investigator according to the CTCAE. When specific adverse events are not listed in the CTCAE they will be graded by the Investigator as *none*, *mild*, *moderate* or *severe* according to the following grades and definitions:

- Grade 0 No AE (or within normal limits)
- Grade 1 Mild; asymptomatic or mild symptoms; clinical or diagnostic observations only; intervention not indicated
- Grade 2 Moderate; minimal, local, or noninvasive intervention (e.g., packing, cautery) indicated; limiting age-appropriate instrumental activities of daily living (ADL)
- Grade 3: Severe or medically significant but not immediately life-threatening; hospitalization or prolongation of hospitalization indicated; disabling; limiting self-care ADL
- Grade 4: Life-threatening consequences; urgent intervention indicated
- Grade 5: Death related to AE

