2.3.2 Secondary Endpoints

- Per patient and per region detection sensitivity and PPV using a combined histology and conventional imaging correlate. *
- Change in management: survey based results. *
- Safety: blood pressure, heart rate, self-reported adverse events. *

Note: * secondary endpoints are assessed at central data analysis in the entire patient

Table 1	
Region	Description
1	Prostate Bed
2	Pelvis outside of prostate bed including lymph nodes
3	Extrapelvic soft tissue, lymph nodes and organ metastases (non-bone)
4	Bone metastases

population (n=1500) across participating institutions (see section 8.3.3)

3 Study Design

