3.1 Number of Subjects

It is anticipated that in study arm 1 up to 750 patients will be enrolled at the University of Michigan in this study. Total population of patients will be 1,500 patients across participating institutions.

The total number of physicians/practitioners (study arm 2) will be small, but theoretically be as high as 750.

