5.2 Monitoring and Toxicity Management

Each patient receiving ⁶⁸Ga-PSMA-11 will be evaluable for safety. The safety parameters include physical findings and spontaneous reports of adverse events reported to the investigator by patients.

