7.2 Evaluation of Safety

Analyses will be performed for all patients receiving ⁶⁸Ga-PSMA-11. The study will use the [CTCAE v4.0](#) for reporting of adverse events.

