7.5 Data and Safety Monitoring

All adverse events will be followed with appropriate medical management until resolved. Patients removed from study for unacceptable adverse events will be followed until resolution or stabilization of the adverse event. For selected cases in which the injection of the investigational radiotracer was stopped (for instance partial or complete paravenous injection), a repeat injection of the subject with the investigational radiotracer may be conducted if considered both safe and ethical by the Investigator.

This trial will be monitored in accordance with the NCI approved University of Michigan Rogel Cancer Center Data and Safety Monitoring Plan. The study team will meet every 3 months or more frequently depending on the activity of the protocol. The discussion will include matters related to the safety of study participants (SAE/UaP reporting), validity and integrity of the data, enrollment rate relative to expectations, characteristics of participants, retention of participants, adherence to the protocol (potential or real protocol deviations) and data completeness. At these regular meetings, the protocol specific Data and Safety Monitoring Report form will be completed and signed by the Principal Investigator or by one of the designated co-investigators.

Data and Safety Monitoring Reports will be submitted to the University of Michigan Rogel Cancer Center Data and Safety Monitoring Committee every 3 months for independent review.

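### Section 7.4 gives two recording rules for adverse events, one naming grade 3 and above and one with no grade limit, while the safety endpoint and its analysis have no grade limit

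*Combined protocol and SAP*

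**What the plan says.** All references are to the combined protocol and SAP.

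- **Recording, opening of 7.4:** "All grade 3 and above adverse events will be recorded using the NCI CTCAE v4.0".
- **Recording, later in 7.4:** "Signs or symptoms reported as adverse events will be graded and recorded by the Investigator according to the CTCAE". For events that the CTCAE does not list, the section then supplies its own scale from grade 0 to grade 5, with definitions for mild (grade 1) and moderate (grade 2) events.
- **Endpoint, 2.3.2:** "Safety: blood pressure, heart rate, self-reported adverse events". The note to that section says that "secondary endpoints are assessed at central data analysis in the entire patient" population, pooled over the participating institutions.
- **Safety parameters, 5.2:** "The safety parameters include physical findings and spontaneous reports of adverse events reported to the investigator by patients".
- **Analysis, 8.3.5 item 5:** a descriptive report of the rates of adverse events that patients report.

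Neither the endpoint nor the analysis item sets a minimum grade.

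**The concern.** Section 7.4 is the protocol's own section on recording adverse events. If every event is to be recorded, the words limiting its first sentence to grade 3 and above do no work, so a coordinator could reasonably take them as a cut-off. The later sentence in the section says otherwise, and nothing states which of the two governs grades 1 and 2.

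At stake is a stated secondary endpoint. An event that was never written down cannot enter a rate. Active safety follow-up ends 1 to 3 calendar days after administration (3.3.1), so a mild event missed then would be hard to recover later. The data are also meant for pooling towards a future NDA, so the recording rule at this site carries into the pooled safety summary.

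The primary PPV analysis does not use these data. Expedited IND reporting (7.6) depends on whether an event is suspected, unexpected and serious, so it does not depend on this sentence. The blood pressure and heart rate parts of the safety endpoint are also untouched.

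**Working it through.** The plan states no adverse event rate and no safety sample size calculation, so there is no figure to reproduce. The check is a comparison of the passages.

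**Step 1. What each passage says about grade.**

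| Place | Subject | Lower grade limit |
|---|---|---|
| 7.4, first sentence | recording | names grade 3 and above |
| 7.4, later sentence | recording | none |
| 7.4, scale for unlisted events | grading | none; grades 1 and 2 defined |
| 2.3.2 | endpoint | none |
| 5.2 | safety parameters | none |
| 8.3.5 item 5 | analysis | none |

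Sections 7.2 and 7.5 add little. The first says whose data are analysed ("Analyses will be performed for all patients receiving" the tracer) and the second concerns medical follow-up ("All adverse events will be followed with appropriate medical management until resolved"). Neither fixes which grades are recorded. Section 6.1.3 asks only for evaluation of adverse events and does not settle the matter.

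**Step 2. Reading A: the first sentence is a threshold.** On a per-patient basis, the rate implied by 2.3.2 and 8.3.5 is

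rate = (patients reporting an adverse event of any grade) / (patients given the tracer).

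With only grade 3 and above on file, what can be computed is

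recorded rate = (patients reporting an event of grade 3 or above) / (patients given the tracer).

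The shortfall is the proportion of patients whose worst reported event is grade 1 or 2. It is never negative, so any bias is downward. It is zero only if there are no such patients. The same holds if events rather than patients are counted.

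**Step 3. Reading B: the first sentence is a minimum and the later one governs.** Every reported event is graded and recorded, the numerator is complete, and the shortfall is zero.

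**Step 4. Which reading the text favours.** The first sentence does not say that only those events are recorded. The later sentence has no limit, and definitions of grades 1 and 2 would have little use if such events were never recorded. The endpoint and the analysis also fit reading B. Reading B is therefore the better one, and the opening of 7.4 is the phrase out of line with it.

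**Step 5. Size.** The shortfall under reading A needs the proportion of patients with grade 1 or 2 events only. The documents do not give it, so no number can be put on it.

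**The case against.** The strongest reply is that 7.4 largely answers itself. The later sentence and the 0 to 5 scale cover mild and moderate events, the opening sentence can be read as a minimum, and the case report forms, which are not in the documents, may already collect every grade. An endpoint list that is silent on grade does not by itself contradict a recording rule set elsewhere. All of this stands, and it keeps the point minor. It does not remove the point, because the two sentences give staff different instructions and the text does not say which one applies.

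A second reply is that the sponsor may have wanted a grade 3 floor. The documents do not exclude that, but the endpoint and the analysis would then have to say so. The passages need reconciling either way.

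Two stronger readings are tempting and are not supported:

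- A reader might infer that the protocol excludes grade 1 and 2 events from the safety data. It does not; most of its text points the other way.
- A reader might note that this site may enrol up to 750 patients and that "Total population of patients will be 1,500 patients across participating institutions", and conclude that 750/1,500 = 50% of the pooled mild and moderate events would be lost. That needs the threshold to be applied here, every other site to record all grades, and event rates to be equal across sites. The documents establish none of these. Section 1.1 says that endpoints were aligned across institutions, so a difference in recording between sites cannot be presumed.

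**Conclusion.** The point holds as an internal inconsistency in 7.4 that bears on a secondary endpoint. Its severity is minor. If the opening sentence is applied as a threshold, the planned rate of self-reported adverse events is understated and cannot be computed as defined. If the later sentence governs, nothing is lost. The protocol as a whole favours the second reading, and no actual loss is shown. The size cannot be estimated from the documents. The conclusion assumes only that staff could act on the first sentence as it stands and that the case report forms, which were not available, do not already settle the question.

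**What to change.** 1. In 7.4, replace the opening reference to grade 3 and above with wording that covers adverse events of any grade, so that recording matches 2.3.2 and 8.3.5 item 5.
2. If a grade 3 floor was truly intended, keep it in 7.4, amend the later sentence there to agree, and state the floor in 2.3.2 and 8.3.5, so that the reported rate is labelled for what it is.
3. In the safety report, state which recording rule applied to subjects already scanned. This matters because the study is under way: 8.2.1 already refers to 316 evaluable subjects.

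The cost is one phrase in the protocol, one sentence in the report and slightly more data entry. No new visit or procedure is needed, since patients are already monitored for two hours after administration (5.1.1.2) and followed for adverse events at 1 to 3 days (3.3.1).

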7.5 Data and Safety Monitoring

All adverse events will be followed with appropriate medical management until resolved. Patients removed from study for unacceptable adverse events will be followed until resolution or stabilization of the adverse event. For selected cases in which the injection of the investigational radiotracer was stopped (for instance partial or complete paravenous injection), a repeat injection of the subject with the investigational radiotracer may be conducted if considered both safe and ethical by the Investigator.

This trial will be monitored in accordance with the NCI approved University of Michigan Rogel Cancer Center Data and Safety Monitoring Plan. The study team will meet every 3 months or more frequently depending on the activity of the protocol. The discussion will include matters related to the safety of study participants (SAE/UaP reporting), validity and integrity of the data, enrollment rate relative to expectations, characteristics of participants, retention of participants, adherence to the protocol (potential or real protocol deviations) and data completeness. At these regular meetings, the protocol specific Data and Safety Monitoring Report form will be completed and signed by the Principal Investigator or by one of the designated co-investigators.

Data and Safety Monitoring Reports will be submitted to the University of Michigan Rogel Cancer Center Data and Safety Monitoring Committee every 3 months for independent review.

7.6 Expedited Reporting

Reporting to the Institutional Review Board

If a death occurs during the treatment phase of the study or within 30 days after the last administration of the study drug(s) and it is determined to be related either to the study drug(s) or to a study procedure, the Investigator or his/her designee must notify the University of Michigan IRB within 1 business day of knowledge of the event. The contact may be by phone or e-mail.

Expedited Reporting to the Food and Drug Administration

As the study is being conducted under an IND, the Sponsor-Investigator is responsible for determining whether or not the suspected adverse reaction meets the criteria for expedited reporting in accordance with Federal Regulations (21 CFR §312.32).

The Investigator must report in an IND safety report any suspected adverse reaction that is both serious and unexpected. The Sponsor-Investigator needs to ensure that the event meets all three definitions:

- Suspected adverse reaction (as defined in 7.3.2.1)
- Unexpected (as defined in 7.3.2.2)
- Serious (as defined in 7.3.2.3)

If the adverse event does not meet all three of the definitions, it should not be submitted as an expedited IND safety report.

The timeline for submitting an IND safety report to FDA is no later than **15 calendar days** after the Investigator determines that the suspected adverse reaction qualifies for reporting (21 CFR 312.32(c)(1)).

Any unexpected fatal or life-threatening suspected adverse reaction will be reported to FDA no later than **7 calendar days** after the Investigator's initial receipt of the information (21 CFR 312.32(c)(2)).

Any relevant additional information that pertains to a previously submitted IND safety report will be submitted to FDA as a Follow-up IND Safety Report without delay, as soon as the information is available (21 CFR 312.32(d)(2)).

8 Statistical Considerations and Evaluation of Results

8.1 Study Endpoints

- Per patient ⁶⁸Ga-PSMA-11 positivity.
- Histological correlation with ⁶⁸Ga-PSMA-11 lesion results.

8.1.1 Randomization

There will be no randomization performed. There will be no blinding performed.

8.2 Determination of Sample Size and Accrual Rate

8.2.1 Sample Size and Power Estimate

The primary endpoint is to evaluate the positive predictive value (PPV) (true positives / (true positives + false positives)) of ⁶⁸Ga-PSMA-11 PET for presence or absence of prostate cancer

confirmed by histopathology on a per-patient basis. It is anticipated that – on a per-patient basis – the PPV of conventional imaging ranges between 30-50%. An overall PPV for ⁶⁸Ga-PSMA-11 PET of at most 50% will be considered as unacceptably low. Hence, the null hypothesis that the PPV is at most 50% will be tested against the alternative hypothesis that the PPV is greater than 50%.

Given recently published data from ⁶⁸Ga-PSMA-11 indicating a substantially higher PPV than previously assumed ⁴¹, we now hypothesize that ⁶⁸Ga-PSMA-11 PET imaging will substantially increase the PPV to at least 75% in our patient population.

We previously expected that approximately 25% of the accrued patients will undergo a biopsy and 95% of the biopsied patients will have positive ⁶⁸Ga-PSMA-11 PET scan at the biopsied site (about 5% of patients may receive a biopsy of a ⁶⁸Ga-PSMA-11 negative site, which was however identified on conventional imaging). However, we were able to obtain biopsies from ⁶⁸Ga-PSMA-11 positive lesions in only 13 of 316 evaluable subjects, and no biopsies of ⁶⁸Ga-PSMA-11 negative lesions identified by conventional imaging were obtained.

When 750 (instead of 375) patients are accrued at the University of Michigan, we now expect that about 24 patients who are to receive a biopsy will receive the biopsy of a ⁶⁸Ga-PSMA-11 positive lesion. Then, the attainable power is estimated at 80% for detecting an increase in the PPV from 50% to 75% at the one-sided 0.05 significance level.

Within the first secondary objective, the region-specific PPV will be determined (confirmed by conventional imaging, clinical follow-up, and/or histopathology/biopsy where available). Based on the results of previous studies, the following distribution of biopsied disease across the four regions are anticipated ^{1,2}:

- a) Prostate bed: 30%
- b) Pelvis: 15%
- c) Extrapelvic soft tissue: 20%
- d) Bone metastases: 35%

In summary, a sample size of 750 UM patients would be sufficient to achieve adequate power for detecting an increase in the per-patient PPV from 50% to 75% for the primary objective. Regarding the first secondary objective (region-specific PPV), the per-region tests would have adequate power in the 1,500 pooled sample from all participating sites.

8.3 Analyses Plans

8.3.1 Analysis Population

Patients with histopathology correlates will be analyzed for the primary aim. All remaining patients will be analyzed for the secondary endpoints.

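### Section 8.3.1, read as written, leaves histology-verified patients out of the secondary analyses, against 2.3.2 and the pooled 1,500 in 8.2.1

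*Combined protocol and SAP*

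**What the plan says.** Section 8.3.1 is the only section headed as defining the analysis population, and it has two sentences. The first reads "Patients with histopathology correlates will be analyzed for the primary aim". The second reads "All remaining patients will be analyzed for the secondary endpoints".

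Three other places name a population:

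- **2.3.2**, in a note split by Table 1 in the extracted text, says "secondary endpoints are assessed at central data analysis in the entire patient" … "population (n=1500) across participating institutions". The first endpoint under that note is per-patient and per-region sensitivity and PPV "using a combined histology and conventional imaging correlate".
- **8.2.1**, closing summary, claims adequate power for the per-region tests in the pooled sample of 1,500.
- **7.2** analyses safety in everyone who received the tracer; 5.2 and 7.1 agree. Safety is a secondary endpoint in 2.3.2.

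Other sections give a reference standard without naming a population. In 8.2.1 the "region-specific PPV will be determined (confirmed by conventional imaging, clinical follow-up, and/or histopathology/biopsy where available"). Section 2.2 uses a similar composite. Section 8.3.5 item 1 uses histopathology plus imaging follow-up for PPV; item 2 names histopathology or biopsy alone for sensitivity.

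**The concern.** In 8.3.1, coming straight after the patients who have histopathology, the word *remaining* can only mean those who do not. An analyst looking up the population there would build the secondary dataset without the biopsied patients. The combined-reference PPV would then contain no histology and would rest wholly on the follow-up rules in 8.3.4 b, under which a positive lymph node or bone lesion that does not meet the true-positive criteria is called false positive. Sensitivity under 8.3.5 item 2 would lose the patients on whom it depends.

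The data are to be pooled across sites for a marketing application. If Michigan applied 8.3.1 literally and other sites did not, one pooled estimate would mix two population rules.

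**Working it through.** **1. Which statements actually conflict**

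| Section | Names a population? | Agrees with 8.3.1 as written? |
|---|---|---|
| 2.3.2 note | Yes: everyone, 1,500 | No |
| 8.2.1 closing summary | Yes: pooled 1,500, per-region tests | No |
| 7.2 (with 5.2, 7.1) | Yes: everyone given tracer, safety | No, but the safety rule itself is clear |
| 2.2; 8.2.1 reference standard; 8.3.5 items 1–2 | No: reference standard only | Indirect evidence against it |

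Section 2.3.2 refers the reader to 8.3.3, which describes the central read and names no analysis population. The PSA-stratified detection rate (2.2 and 8.3.5 item 3) is not listed among the endpoints in 2.3.2, so only the general wording of the note covers it.

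**2. Patients removed at Michigan if 8.3.1 is followed literally**

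Inputs, all from 8.2.1: 750 patients; about 24 expected to have a biopsy of a PSMA-positive lesion; biopsies so far from "positive lesions in only 13 of 316 evaluable subjects".

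- Protocol estimate: 24/750 = 3.2%, leaving 726.
- Observed rate: 13/316 = 4.11%; 4.11% × 750 = 30.9, about 31; 31/750 = 4.1%, leaving 719. This assumes the rate continues and all 750 are evaluable.

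The plan's 24 is lower than its own observed rate implies, so both are carried as a range. As a share of the pooled 1,500, if only Michigan applies the rule: 24/1500 = 1.6% to 31/1500 = 2.1%. The documents give no biopsy rate for the other sites.

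**3. Effect on the overall detection rate**

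Let *n* be the patients, *p* the overall detection rate and *b* the number removed, all taken as PSMA-positive. The rate falls from *p* to (*np* − *b*)/(*n* − *b*), a drop of *b*(1 − *p*)/(*n* − *b*).

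| *p* | *b* = 24 | *b* = 31 |
|---|---|---|
| 85% | 3.6/726 = 0.5 points | 4.65/719 = 0.6 points |
| 50% | 12/726 = 1.7 points | 15.5/719 = 2.2 points |

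The two values of *p* are assumptions. Section 1.2 cites 50% for PSA below 1 ng/ml and above 85% for PSA above 2 ng/ml, so 50% overall is the low end. Shifts within the five PSA bands cannot be computed, because neither band sizes nor biopsies per band are given.

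**4. Effect on PPV and sensitivity**

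- Composite PPV (8.3.5 item 1): the histology contribution goes to zero and imaging follow-up remains.
- Sensitivity (8.3.5 item 2): histopathology is the only confirmation named, so removing every patient with histopathology leaves 0 evaluable patients. This needs every biopsied patient to count as having a histopathology correlate, including any with a biopsied PSMA-negative lesion.

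**5. The separate sensitivity mismatch**

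Section 8.2.1 adds that no biopsies of PSMA-"negative lesions identified by conventional imaging were obtained" among those 316 subjects. With biopsied patients restored, histology-only sensitivity is TP/(TP + FN), and with FN = 0 it equals TP/TP = 100% whatever the scanner misses. Sections 8.3.4 b and 8.3.4 c leave routes by which false negatives could still arise, so this is conditional on the pattern continuing.

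**6. Primary analysis**

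Its population is the first sentence of 8.3.1, which is not in dispute. The stated 80% power with about 24 biopsied patients is untouched.

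**The case against.** The strongest reply is that the intent is plain. Section 2.3.2 states the population and its size, 8.3.5 is headed as the central analysis of the secondary endpoints, and 8.2.1 refers to the pooled 1,500. A literal reading would also empty 8.3.5 item 2, which suggests loose drafting. On this view the point is a wording clarification affecting a few percent of patients.

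Much of that stands. The sponsor probably does mean all patients, and the numerical effect is small. But no order of precedence is stated, and 8.3.1 is where a reader looks for the population. Intent inferred from other sections does not replace a correct rule.

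Four stronger readings are tempting, and the documents do not support them:

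- *That 8.3.1 expressly restricts the secondary endpoints to unbiopsied patients.* It contains no such explicit restriction; the exclusion follows from the word *remaining*.
- *That every section mentioning histopathology contradicts 8.3.1.* Sections 2.2 and 8.3.5 items 1–2, and the reference standard in 8.2.1, name no population and are indirect support.
- *That the safety population is in doubt.* Sections 5.2, 7.1 and 7.2 settle it.
- *That sensitivity is empty on any reading.* If patients with a biopsied PSMA-negative lesion were treated as remaining, because they cannot contribute to a PPV, item 2 could contain false negatives alone. Section 8.3.1 also does not say whether a negative biopsy resolved by imaging under 8.3.4 c counts as a histopathology correlate, so the counts above are approximate.

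**Conclusion.** The point holds as a contradiction between stated populations: 8.3.1 against 2.3.2 and the closing summary of 8.2.1, and, in wording only, against 7.2. It should be corrected before analysis.

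Its importance is qualitative. One secondary analysis would lose the component that gives it its name, and another would have no data on the reading set out above. The loss of about 24–31 of 750 Michigan patients assumes literal use of 8.3.1 and either the protocol's estimate or a continuing 13/316 biopsy rate. The detection-rate shifts further assume that all removed patients are PSMA-positive. A large bias in the secondary results, or any effect on the primary result, is not supported.

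The histology-only sensitivity reference in 8.3.5 item 2 is a second, separate mismatch with 2.2 and 2.3.2. Correcting 8.3.1 alone would not resolve it.

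**What to change.** Replace the second sentence of 8.3.1 with one saying that every patient, those with histopathology correlates included, enters the secondary analyses. Add that PPV and sensitivity are evaluated in patients who have the applicable reference standard, and safety in all who received the tracer, as 7.2 already states. It would help to define histopathology correlate, covering biopsied PSMA-negative lesions and negative biopsies resolved by follow-up imaging.

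Separately, reconcile the sensitivity reference in 8.3.5 item 2 with the composite in 2.2 and 2.3.2. If histology alone is kept, state that sensitivity will be near 100% by construction unless PSMA-negative lesions are biopsied.

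The cost is one reworded sentence, a short statement of the populations and a one-line decision on the reference. No new data are needed, and the primary analysis does not change.
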